### 5.3.4.2. Analysis Methods

The analysis of the time to first-line treatment of MM will be similar to the analysis of primary endpoint PFS described above.

## 5.3.5. Progression-free Survival on First-line Therapy for MM

### 5.3.5.1. Definition

Progression-free survival on first-line therapy (PFS2) is defined as the time from randomization to progression on first-line therapy or death, whichever comes first. Disease progression will be based on investigator assessment. Any deaths are considered as PFS2 events. Subjects who start first-line therapy without disease progression on study treatment will be censored at the last disease assessment on or before starting first-line therapy. Subjects who start first-line therapy after progression on study treatment, are still alive and not yet progress on first-line therapy, will be censored at the last date of follow-up or the day before the start date of 2nd line of next therapy, whichever comes first. Subjects without any post-baseline follow-up will be censored at the randomization. Subjects who were already diagnosed multiple myeloma per baseline central imaging review will be censored at randomization.

Determination of dates of PFS2 event and dates for censoring is summarized in [Table 5](#) as follows.

**Table 5: PFS2 Event and Censoring Method**

Situation	Date of Progression or Censoring	Outcome
No post-baseline disease assessment	Randomization	Censored
Alive and no disease progression on study treatment	Date of last disease assessment on or prior to start of 1st line of next therapy	Censored
Disease progression on study treatment and progress on the 1 st line of next therapy or any death	Minimum of earliest date that indicates progression on the 1 st line of next therapy and date of death	PFS2 event
Other	Minimum of start date of 2 nd line of next therapy minus 1 and last date of follow-up	Censored

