2.1.2. Endpoints

Primary Endpoint

The primary endpoint of this study is PFS (defined as the time from the date of randomization to the date of initial documented progression to MM according to the IMWG diagnostic criteria for MM or the date of death, whichever occurs first).

Secondary Endpoints

To demonstrate additional clinical benefit, the following secondary endpoints will be evaluated:

- Time to biochemical or diagnostic (SLiM-CRAB) progression defined as the earlier of time to the earlier of biochemical progression or diagnostic (SLiM-CRAB) progression (see Section 9.2.2)
- Overall response rate (ORR), defined as, the proportion of subjects with a PR or better as defined by the IMWG response criteria
- Complete response (CR) rate, defined as, the proportion of subjects with a CR (or better) as defined by the IMWG response criteria
- Time to first-line treatment for MM, defined as, the time from the date of randomization to the date of the first-line treatment for MM
- Progression-free survival on first-line treatment for MM (PFS2), defined as, the time from the date of randomization to the date of documented progressive disease (PD) on the first-line treatment for MM or death, whichever comes first
- Overall survival (OS), defined as, the time from the date of randomization to the date of death
- Incidence of MM with adverse prognostic features, which include International Staging System Stage III (based on β 2-microglobulin and albumin) and adverse cytogenetic characteristics

- Serum daratumumab PK concentrations and parameters including minimum observed concentration (C_{min}) and maximum observed concentration (C_{max})
- Incidence of anti-daratumumab antibodies and anti-rHuPH20 antibodies
- Change from baseline in global health status and emotional functioning scales of the European Organization for Research and Treatment of Cancer (EORTC) quality of life questionnaire (QLQ)-C30, future perspective scale of the EORTC QLQ-MY20, and utility and visual analog scale of the European Quality of Life Five Dimensions Questionnaire (EQ-5D-5L)
- Duration of response, defined as date of onset of first response until date of disease progression or death
- Time to response, defined as the time from randomization until onset of first response

Exploratory Endpoints

- Identification of novel biomarkers in relation to PFS/OS

Refer to Section 9, Study Evaluations for evaluations related to endpoints.

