For subjects randomized to active monitoring (Arm A), no disease-specific treatment will be given and subjects are to be evaluated every 12 weeks. For subjects randomized to daratumumab (Arm B), daratumumab SC (daratumumab 1800 mg + rHuPH20 [2000 U/mL]) will be administered weekly in Cycles 1 and 2, then every 2 weeks for Cycle 3 to Cycle 6, and every 4 weeks thereafter until 39 cycles or up to 36 months or confirmed PD (or other reasons as outlined in Section 10), whichever occurs first. All subjects in the daratumumab group will be observed for at least 6 hours after the end of the SC injection during Cycle 1 Day 1 and, if deemed necessary by the investigator, after subsequent injections. Based on the data available as of October 2017 from Study MMY1004, no subject has had an IRR with an onset >6 hours after daratumumab SC injection (IB Daratumumab 2017 ¹¹). Measures to prevent IRRs include predose medication with methylprednisolone, paracetamol, and an antihistamine. Montelukast may also be added as a predose medication at the investigator's discretion. Methylprednisolone also will be administered after daratumumab administration with the intention of preventing delayed IRRs.

The Follow-up Phase will begin once a subject completes 39 cycles or 36 months (whichever occurs first) or discontinues active monitoring (Arm A) or daratumumab treatment (Arm B) and completes the End-of-Active Monitoring Visit (Arm A) or End-of-Treatment Visit (Arm B). In both groups, disease evaluation will continue every 12 weeks thereafter until disease progression, as indicated in the Time and Events Schedule (Table 1). The Follow-up Phase for each subject will continue until death, lost to follow up, consent withdrawal, or study end, whichever occurs first.

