10. SUBJECT COMPLETION/DISCONTINUATION OF STUDY TREATMENT/ WITHDRAWAL FROM THE STUDY

10.1. Completion

In the Active Monitoring group, a subject will be considered to have completed the study treatment if the subject has completed 36 months of Active Monitoring. In the daratumumab group, a subject will be considered to have completed study treatment if the subject has completed 39 cycles of therapy or 36 months of daratumumab, whichever occurs first. A subject will be considered to have completed the study (study completion defined in Section 17.9.1) if he or she has been followed to the end of the study or has died before the end of the study. Subjects who have been lost to follow-up, or have withdrawn consent for study participation before the end of the study, will not be considered to have completed the study.

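### The PFS2 rules count progression on first-line therapy only if the first progression was 'on study treatment', so first progressions after month 36 or after early discontinuation lose their PFS2 event

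*SAP*

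**What the plan says.** Protocol 2.1.2 defines PFS2 as running from randomization "to the date of documented progressive disease (PD) on the first-line treatment for MM or death". It sets no condition on when the first progression occurred. The opening sentence of SAP 5.3.5.1 is equally unconditional.

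The rules that follow it add a condition:

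- SAP 5.3.5.1: "Subjects who start first-line therapy without disease progression on study treatment will be censored", at the last disease assessment on or before that therapy.
- SAP 5.3.5.1, for continued follow-up: "Subjects who start first-line therapy after progression on study treatment, are still alive and not yet progress on first-line therapy".
- Table 5 row 2 (censored): "Alive and no disease progression on study treatment".
- Table 5 row 3 (event) opens: "Disease progression on study treatment and progress on the 1", and then continues to the first line of next therapy or any death.

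Deaths are protected: "Any deaths are considered as PFS2 events".

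The treatment and active monitoring phases each last 36 months (Protocol 3.1). For the control arm, Protocol 10.1 says "a subject will be considered to have completed the study treatment if the subject has completed 36 months of Active Monitoring". After that phase, "In both groups, disease evaluation will continue every 12 weeks thereafter until disease progression" (Protocol 3.1), and the study runs about 8 years (Protocol 17.9.1).

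**The concern.** First progressions after month 36 are planned for and will be documented. Take a subject who completes the 36 months, has first PD documented at month 44, starts first-line therapy and later progresses on it while alive. Under the protocol this is a PFS2 event at the second progression. Under Table 5 the subject fits row 2 and is censored near month 44. The same happens to a subject who stops daratumumab early and progresses afterwards.

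This is a different case from therapy started without any documented progression. Here the progression is documented, but after the treatment phase has ended.

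PFS2 is second in the alpha-controlled hierarchy and is tested ahead of OS (SAP 5.1.1). A rule that removes true events according to when the first progression occurred can distort that comparison.

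**Working it through.** **Inputs.** Protocol 11.2: median PFS 30 and 48 months, median PFS2 72 and 96 months (HR 0.75), 180 subjects per arm, 24-month accrual, 134 PFS2 events expected at the end of study. Protocol 17.9.1: end of study about 96 months after the first randomization, so 72 to 96 months of follow-up per subject. The documents give no dropout rate; 0, 5 and 8% per year are my assumptions.

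**The plan's own figures.** PFS power with 165 events at HR 0.625: Φ(−ln 0.625 × √165/2 − 1.96) = Φ(1.06) = 85.5%, against at least 85% stated. Probability that the estimated PFS2 HR is below 1 with 134 events at HR 0.75: Φ(−ln 0.75 × √134/2) = Φ(1.67) = 95.2%, against more than 95% stated. Both reproduce.

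**First progressions after month 36.** With exponential PFS, the share still progression-free at 36 months is 0.5^(36/30) = 43.5% in Arm A and 0.5^(36/48) = 59.5% in Arm B. Averaged over uniform accrual to the 96-month cut, without dropout:

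- Arm A: 52.2 of 153.8 first progressions are late (33.9%).
- Arm B: 53.2 of 126.2 are late (42.2%).

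**PFS2 events that follow a late first progression.** I added an exponential gap after first progression, set so that median PFS2 is 72 and 96 months (median gap 29.5 and 32.0 months). Per 180 subjects at the 96-month cut:

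| Assumed dropout per year | Arm A | Arm B | Both arms |
|---|---|---|---|
| 0% | 24.1 of 104.5 (23.0%) | 22.2 of 77.6 (28.6%) | 46.3 of 182.1 (25.4%) |
| 5% | 18.3 of 86.3 (21.2%) | 16.8 of 63.3 (26.5%) | 35.1 of 149.6 (23.5%) |
| 8% | 15.3 of 76.6 (20.0%) | 14.1 of 56.0 (25.1%) | 29.4 of 132.6 (22.2%) |

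These are upper bounds, because they treat every affected event as a progression. If half were deaths, which still count, the no-dropout loss would be 46.3/2 = 23.2 of 182.1, or 12.7%. Hence roughly 13-25%. Progression after early daratumumab discontinuation is not included and would add to the Arm B loss.

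**Primary analysis (48-month cut).** About 0.4 events per arm are affected, 1.2% and 1.5% of PFS2 events. This is negligible.

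**Direction if active monitoring counts as study treatment (Protocol 10.1).** The loss is a larger share of Arm B events, and the modelled Cox HR moves from about 0.65 to 0.60-0.62, slightly toward daratumumab.

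**Direction if it does not.** SAP 1.2 and Protocol 10.2 name active monitoring for Arm A and study treatment for Arm B as separate things, and Protocol 6 says that Arm A receives no study medication. On that reading no Arm A subject can progress on study treatment. Every first-line progression in a living Arm A subject would be censored, and the heavier loss falls on Arm A.

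**The case against.** The strongest defence is that the phrase is a sequence label: first progression on study, as opposed to progression on the next therapy. The unconditional opening sentence of SAP 5.3.5.1 supports this, and so does SAP 5.3.5.2, which schedules visits after initial PD with no on-treatment limit. The odd result for Arm A under the strict reading also suggests that no calendar restriction was meant. This may well be the intention, but the SAP does not say so. SAP 5.2.2 treats treatment discontinuation and study discontinuation as separate events, and the condition appears twice in the text and in two table rows. A programmer who follows the rules would censor these subjects.

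Three stronger inferences are tempting, and the documents do not support them:

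- **A reader might infer a fixed bias toward daratumumab.** It holds only if active monitoring is study treatment, and the documents point both ways. Even then the numbers lost are nearly equal, 24 and 22 per 180; only the shares differ.
- **A reader might take the HR shift as the trial's own.** The model gives about 182 events and a baseline HR of about 0.65, where the protocol has 134 and 0.75. The gap distribution is assumed. The shift is illustrative only.
- **A reader might infer that lost events cut the alpha spent.** Without dropout, 182.1 − 46.3 = about 136 events remain against the 134 expected, so full alpha is still spent. At the primary analysis the effect is 0.8/134 × 0.05 = 0.0003. At an assumed 5% dropout the upper-bound loss would leave about 115 events, but no dropout rate is stated, so the point does not rest on this.

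**Conclusion.** The rule is wrong as written. Followed literally, SAP 5.3.5.1 and Table 5 censor living subjects whose documented first progression came after month 36 or after early daratumumab discontinuation. That conflicts with Protocol 2.1.2 and with the SAP's own opening definition.

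The effect bears on the final PFS2 analysis. If PFS2 is rejected at the primary analysis, it is not tested again (SAP 5.1.1), and the problem then touches only later estimates. The size given rests on exponential PFS, an assumed exponential gap, the protocol's medians and full follow-up to 96 months. The textual conflict does not depend on the model. The direction of bias cannot be stated until the term is defined, which is itself a reason to remove it from a hierarchical endpoint.

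**What to change.** In SAP 5.3.5.1 and in Table 5 rows 2 and 3, replace *on study treatment* with *at any time after randomization, on or off study treatment or active monitoring (initial PD)*. Row 2 then reads *Alive and no initial PD*. Row 3 reads *Initial PD and progression on the 1st line of next therapy, or any death*.

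The cost is one phrase in the text and in two table rows, with a matching check of the PFS2 derivation program. No new data are needed, since Protocol Table 1 already collects PFS2 in post-PD follow-up. If the phrase was only ever a sequence label, the change leaves the intended analysis as it is.

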
Table 1: Time and Events Schedule
 
9.2 Efficacy Evaluations
 
9.2.3 CRAB Criteria-related Laboratory Assessments
 
9.2.4 Myeloma Protein Measurements in Serum and Urine
 
9.2.5 β2-microglobulin and Lactate Dehydrogenase
 
9.2.6 Bone Marrow Examination
 
Assessment of Bone Disease
 
9.7 Safety Evaluations
 
9.5 Patient-reported outcomes
 
9.6 Medical Resource Utilization
	
Central laboratory testing will be discontinued.
 
Pre-PD follow up and PD assessments:
 
 • Disease evaluations should continue according to Time & Events Schedule, by local assessment • Only disease progression by investigator via local assessment will be reported to the Sponsor. • Assessment of response for disease evaluations and local laboratory and imaging results will not be reported to the Sponsor. 
Post-PD follow-up:
 
PRO and MRU collection at Months 12 and 18 in the have been discontinued.
	
Post primary analysis, central laboratory testing and central imaging are no longer required.
 
Post primary analysis, PRO and MRU collection at Months 3 and 6 are considered sufficient.

Table 1: Time and Events Schedule
 
9.4 Biomarkers
 
Table 10
	
Central Laboratory Biomarker assessments will be discontinued.
	
Post primary analysis, biomarker analyses are no longer required.

9.3 Pharmacokinetics and Immunogenicity
	
Immunogenicity and PK assessments will no longer be collected.
	

SYNOPSIS
 
Table 1: Time and Events Schedule
 
Table 2: Daratumumab Administration (Arm B Only)
 
9.1.1 Overview
 
9.2 Efficacy Evaluations
 
9.3.2 Analytical Procedures
 
9.4 Biomarkers
 
9.5 Patient-reported Outcomes
 
9.6 Medical Resource Utilization
	
Home health care visits have been removed throughout the protocol.
	
Home health care visits are no longer available.
 
NOTE: Tele health visits (conducted via phone or video conference) may continue as deemed necessary.

11.12 Data Monitoring Committee
	
The IDMC will be discontinued once the primary analysis endpoint has been achieved.
	
IDMC will no longer be required.

Throughout the protocol
	
Minor grammatical, formatting, or spelling changes were made.
	
Minor errors were noted.

SYNOPSIS

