9.1.4. Follow-Up Phase

The Follow-up Phase will begin once the subject completes 39 cycles or 36 months (whichever occurs first) of active monitoring (Arm A) or daratumumab treatment (Arm B). Reasons for premature discontinuation of active monitoring or daratumumab treatment are listed in Section 10.2. Subjects who discontinue before PD must continue to have disease evaluations as described in Section 9.2, until study completion or confirmed PD (or other reasons as outlined in Section 10). If subjects have not progressed to MM, then no other treatment for SMM or MM is allowed during the study. Follow-up for first-line MM treatment (including the response to first-line MM treatment), second primary malignancies, and survival status will be obtained as specified in the Time and Events Schedule (Table 1). Survival will be followed until the end of the study and at a frequency of at least every 12 weeks until PD. After PD, survival is to be followed at least every 6 months, until the end of the study.

If PRO or survival information is obtained via telephone contact, then written documentation of the communication must be available for review in the source documents. If the subject has died, then the date and cause of death will be collected and documented in the eCRF.

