9.2. Efficacy Evaluations

Disease assessments will be performed every 12 weeks until PD. A window of ± 7 days around the scheduled assessment date is allowed. For subjects with treatment delays, disease assessments should be performed at the scheduled disease assessment dates. They do not need to be repeated at the time of delayed daratumumab administration. Disease progression, if based on laboratory results only, must be confirmed by a consecutive assessment. A repeated investigation for confirmation of disease progression does not need to occur within a specified timeframe and could potentially occur on the same date (at a later timepoint). However, the original value meeting disease progression and the confirmation value must be consecutive (ie, no intermediate values that do not meet the definition of disease progression). It is not a requirement to have a repeat investigation if disease progression is based on at least 2 of the laboratory tests of Hb, calcium,

renal function and FLC at the same assessment date (eg, when Hb <10 g/dL and creatinine clearance <40 mL/min are present on the same day).

Disease assessments will be performed according to the Time and Events Schedule ([Table 1](#)). Disease evaluations scheduled for treatment days should be collected before study drug is administered. Disease progression to MM will be evaluated using the IMWG diagnostic criteria for MM ([Table 9](#)) (Rajkumar 2014²⁹). For subjects who discontinue active monitoring (Arm A) or daratumumab (Arm B) before PD, disease assessments should be performed according the Time and Events Schedule ([Table 1](#)) until study completion or confirmed PD (or other reasons as outlined in [Section 10](#)).

Per protocol Amendment 6, disease assessments will only be performed locally and locally diagnosed disease progression will be reported based upon study investigator review per IMWG criteria.

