### **5. EFFICACY**

#### **5.1. Analysis Specifications**

##### **5.1.1. Level of Significance**

All hypotheses testing will be conducted at a 2-sided level of significance of 0.05. When required, 95% confidence intervals will be constructed.

The primary hypothesis is to be tested at the 0.05 significance level. If the primary endpoint of PFS is statistically significant at the primary analysis, the following secondary endpoints ordered below will be sequentially tested, each with an overall two-sided alpha of 0.05, by utilizing a hierarchical testing approach as proposed by Tang and Geller (1999) that strongly controls Type I error rate:

- ORR
- PFS2
- OS

If the null hypothesis for any of the endpoints fails to be rejected at the primary analysis time point, then any of the subsequent endpoint(s) listed above will not be tested until the next analysis timepoint, if applicable. If the null hypothesis for an endpoint is rejected at a analysis time point, it will remain being rejected and will not be re-tested at the next analysis timepoint, if any. The significance level for each of the above secondary endpoints will be determined by the alpha-spending function specific to the endpoint. The ORR will only be tested at the primary analysis time point with a 2-sided level of significance of 0.05. For PFS2, and OS, alpha spending at the primary analysis time point and the final analysis point will be determined by a linear alpha spending function based on the observed number of the events at the time, i.e., the cumulative alpha to be spent will be the total alpha (0.05) multiplied by the proportion of the observed number of the events out of the total expected number of the events. For example, if 59% targeted PFS2 events are observed at the primary analysis, the corresponding alpha level will be 0.0295(2-sided)). A total of 134 PFS2 events and a total 107 OS events are expected at the final analysis.

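### At the final cutoff, PFS2 may censor progression-free subjects at dates that stop near Amendment 6, while their later deaths and progressions on first-line therapy still count

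*SAP*

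**What the plan says.** SAP 5.3.5.1 and Table 5 use two clocks for PFS2. The row for subjects alive with no progression on study treatment censors at the "Date of last disease assessment on or prior to start of 1st line of next therapy". Subjects who have progressed but have no PFS2 event fall in the last row: "Minimum of start date of 2 nd line of next therapy minus 1 and last date of follow-up". On events, the section says "Any deaths are considered as PFS2 events".

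The prose of 5.3.5.1 is narrower than the table. It states the last-assessment rule only for subjects who start first-line therapy without progression, and gives no rule for those who stay progression-free and untreated.

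The latest SAP version is dated 16 December 2020. Protocol Amendment 6 is dated 9 September 2024. Its summary of changes keeps disease evaluations on schedule by local assessment, then says "Only disease progression by investigator via local assessment will be reported to the Sponsor" and "Assessment of response for disease evaluations and local laboratory and imaging results will not be reported to the Sponsor". Section 9.2 of the protocol body agrees: "locally diagnosed disease progression will be reported based upon study investigator review per IMWG criteria". Section 9.2.1 ends the collection of response. Section 9.1.4 keeps a dated contact: "Survival will be followed until the end of the study and at a frequency of at least every 12 weeks until PD".

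PFS2 is tested after ORR and before OS, at the primary analysis and, if not yet rejected, at the final one (SAP 5.1.1): "A total of 134 PFS2 events and a total 107 OS events are expected at the final analysis".

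**The concern.** The censoring rule was written when every 12-weekly evaluation, positive or negative, reached the database. Under Amendment 6 the sponsor hears of a progression but not of an evaluation that shows none. If the date of a negative evaluation is not recorded either, the last disease assessment of a progression-free subject stays fixed while the study runs on. A subject who later dies, or who progresses and then fails first-line therapy, still contributes the full time and the event. A subject who stays well contributes nothing after the freeze.

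Whether late follow-up counts then depends on the outcome, so the censoring is informative. It removes event-free time only, and more of it in the arm with more progression-free subjects. At stake are the final PFS2 test, the OS test behind it, and the PFS2 curves and hazard ratio in the end-of-study addendum. The number of PFS2 events is the same under either rule, so reaching 134 events would not reveal the problem.

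**Working it through.** **1. The protocol's own figure.** Protocol 11.2 gives more than 95% probability of an estimated PFS2 HR below 1 with 134 events and a true HR of 0.75. SE(log HR) = 2/√134 = 0.173, and Φ(0.2877/0.173) = Φ(1.665) = 0.952. This reproduces. The count of 134 does not follow without dropout: exponential medians of 72 and 96 months, 24-month accrual and a cutoff at month 96 give about 181 events. About 10% dropout per year would be needed, which the documents do not state. Results are therefore shown with and without dropout.

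**2. Who is affected.** Inputs: 180 per arm, 24-month uniform accrual, end at month 96 (8 years), PFS medians of 30 and 48 months. With follow-up of 72 to 96 months and median m, the share still alive and progression-free is

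(m/ln 2)/24 × (2^(−72/m) − 2^(−96/m)).

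- Arm A: 43.28/24 × (0.1895 − 0.1088) = 0.145, or about 26 of 180.
- Arm B: 69.25/24 × (0.3536 − 0.2500) = 0.299, or about 54 of 180.

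A 12-month gap thus drops about 26 and 54 person-years. Events are unchanged.

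**3. Length of the gap (assumed).** The first randomization date is not given. The protocol history starts on 19 July 2017, so 8 years ends in July 2025 at the earliest, about 10 months after the date of Amendment 6. A first randomization 8 months after that protocol makes it about 18. Protocol 17.1 bars implementation before ethics approval, so the effective gap at a site is shorter. A range of about 5 to 18 months is taken.

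**4. Effect on the HR.** Simulated trials of 360: exponential PFS with medians 30/48, and post-progression time set so that the PFS2 medians are 72/96. Both sets of censoring dates were applied to the same trials. Here 15% of PFS events are deaths (assumed), and power is at two-sided 0.05.

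| Dropout | Gap (months) | HR, current dates | HR, dates stopped | Power, current | Power, stopped |
|---|---|---|---|---|---|
| none (about 182 events) | 6 | 0.669 | 0.680 | 0.758 | 0.711 |
| | 12 | 0.667 | 0.692 | 0.757 | 0.682 |
| | 18 | 0.673 | 0.715 | 0.767 | 0.617 |
| 7% per year (about 140 events) | 6 | 0.665 | 0.674 | 0.668 | 0.640 |
| | 12 | 0.668 | 0.689 | 0.664 | 0.593 |
| | 18 | 0.670 | 0.705 | 0.664 | 0.536 |

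The shifts run from 0.009 to 0.042. With 10% dropout per year and 10% deaths (about 127 events), they are 0.005 to 0.010 for gaps of 4 to 7 months and about 0.015 to 0.03 for 10 to 18 months. Power then falls by about 1 to 4 and 4 to 10 points.

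Two cautions apply. The two-stage model gives a current-date HR of 0.65 to 0.67 rather than 0.75 although the medians match, so read the shift and not the level. Alpha spent at the primary analysis lowers the final nominal level below 0.05, so read the fall in power and not its level.

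**5. Curves.** Without dropout and with gaps of 10 to 18 months, estimated PFS2 at 84 months falls from 0.40 to 0.36–0.38 in Arm A and from 0.55 to 0.47–0.51 in Arm B.

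**6. Direction.** If PFS is equal in both arms, lost time is equal and the HR stays at about 1.00. If PFS differs but both PFS2 medians are 72 months, the HR moves from 1.00 to 1.06 (12 months) or 1.10 (18 months).

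**The case against.** The strongest objection is that the decisive step is an inference. Amendment 6 says that results are not reported; it does not say that the date of a negative evaluation goes unrecorded. Evaluations continue every 12 weeks, Protocol 9.6 still enters resource use in the eCRF at disease assessment visits, and survival contacts continue. A reader might infer that no assessment date exists after Amendment 6 for any progression-free subject. The documents do not support that. Equally, they nowhere confirm that such a date is captured, and neither document makes a visit or contact date the PFS2 censoring date. The point therefore stands as a conditional one.

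Second, if the Table 5 row is read in line with the prose, progression-free untreated subjects fall under the last row and are censored at last follow-up, and the problem disappears. The row's label is broader than the prose, so both readings are open. That ambiguity needs settling in any case.

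Third, the shift is small against sampling error: ln(0.715/0.673) = 0.061, about a third of the SE of 0.173. That is fair for a single estimate. The shift is systematic, though, and the fall in power is not negligible at the longer gaps.

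Fourth, the error works against daratumumab. This stands: it cannot create a false claim of benefit, and the primary PFS analysis was complete before Amendment 6.

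**Conclusion.** The mismatch between Table 5 and Amendment 6 is real. Applied as written at the final cutoff, and unless negative-evaluation dates are captured, the rule gives informative censoring, heavier in Arm B. The HR moves toward 1 by roughly 0.01 to 0.04 for gaps of about 5 to 18 months, both PFS2 curves are pulled down, and some power is lost. The size rests on assumptions the documents do not fix: the gap, dropout of 0 to 10% per year, 5 to 20% of first events being deaths, and the exponential two-stage model.

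A reader might infer that a confirmatory test is bound to be affected. SAP 5.1.1 does not support that. PFS2 is tested only if PFS and ORR were rejected, ORR is tested only at the primary analysis, and a PFS2 rejection there is final. Only if PFS2 failed at the primary analysis do its final test, and OS behind it, depend on this rule. In every other case the effect is on the end-of-study estimates reported in the addendum.

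**What to change.** Before the final cutoff:

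- Confirm whether the eCRF still records the date of each negative local evaluation. If it does not, add one item at the existing 12-weekly contact: date of the last local disease evaluation, PD yes/no. Censor progression-free subjects there for PFS2.
- If that date cannot be obtained, amend the second row of Table 5 to censor at the last follow-up contact, on or before the start of first-line therapy, at which no progression had been reported.
- Align the 5.3.5.1 prose with the table so that progression-free subjects who never start therapy have an explicit rule.
- Keep the present rule as a sensitivity analysis.
- For any update of PFS by investigator, use only a recorded evaluation date. Progression is itself the event there, and a survival contact is not a disease assessment.

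The cost is one eCRF date or one SAP row. The downside is small: a contact date is weaker evidence of no progression than a documented assessment, which is why the evaluation date comes first.
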